2.1.1 Effectiveness

[figure not shown]
The effectiveness and relevance of aesthetically pleasing outcomes following Belotero Balance injection will be established in the following manner:

- The primary endpoint (see [Section 2.2.1](#)) will establish effectiveness by using the MIHAS to demonstrate that clinically relevant changes of ≥ 1 -point on both IOHs can be detected 2-months post-treatment.
- The secondary endpoints (See [Section 2.2.2](#)) including the validated FACE-Q satisfaction with eyes, the investigator GAIS, and the subject GAIS will be utilized to substantiate aesthetically pleasing outcomes. The GAIS assessments will be used in the treated subjects only. Improvements in the FACE-Q satisfaction with eyes scores from baseline to 2-months post-treatment will indicate that subjects are satisfied with treatment effects observed on their IOHs and such changes are considered to be clinically relevant from the subject's perspective. Responses for FACE-Q satisfaction with eye scores in the control group will be compared to that of the treatment group in order to show that changes in satisfaction post-treatment are clinically relevant to the subject.

Additionally, the investigator and subject GAIS scores at Month 2 post last injection will be utilized to demonstrate the level of improvement, when compared to baseline photographs, resulting from treatment in the IOHs.

- The level of agreement in treated subjects between the MIHAS responders (≥ 1 -point improvement on both IOHs), [REDACTED] and the level of improvement (score of ≥ 1) on the treating investigator- and subject-GAIS assessments will be obtained. Aesthetically pleasing outcomes that are clinically relevant will be established if the agreement between the MIHAS responders and the level of improvement on the investigator- and subject-GAIS scores, respectively, are met as per the pre-defined endpoints in [Section 2.2.3](#).

In totality, the results from the MIHAS, as well as the supportive outcomes obtained from the treating investigator and subject perspectives regarding aesthetic improvements, will be used to establish that Belotero Balance injections in the IOH region are effective in producing clinically relevant and aesthetically pleasing outcomes.

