If subjects report a safety concern during the 72-hour phone call, an unscheduled visit will be scheduled to bring the subject into the clinic to address safety concerns.

Control-group subjects will be evaluated at enrollment and Month 2 in the clinic. The only effectiveness assessment that will be performed in the control group is the [REDACTED]

[REDACTED] FACE-Q instruments. No investigator GAIS will be performed with control subjects, nor will these subjects self-report on the GAIS.

Section 5.1 and Appendices 10.1 (treated subjects) and Appendix 10.2 (control subjects) detail a full schedule of study events and a schedule of events for each visit.

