made to have the same study personnel take photographs at every visit throughout the study. Photography procedures will be described in a separate user manual. The photographic lighting for this study will replicate that of the images used in the validated photo-numeric MIHAS; strobes will be set at fixed superior-oblique positions relative to the subject's face specifically located to illuminate the IOH target area for evaluation.

3.2.1.3 *Treating investigator Global Aesthetic Improvement Scale (GAIS)*

The treating investigator will use the GAIS to assess global aesthetic improvement among treated subjects using baseline, pre-treatment photos for comparison to Month 2 after the last injection (i.e., either baseline treatment or touch-up, if applicable) (see [Table 1](#)). The GAIS will not be completed for subjects randomized to the control group. The treating investigator must perform the GAIS rating based on the current cosmetic result for both IOHs based on photographic assessments. Investigators are to use photographs taken at baseline before injection to make a comparison to the cosmetic result at Month 2 after the last injection (i.e., either baseline treatment or touch-up, if applicable). The following 7-point scale will be used:

[figure not shown]
[figure not shown]
Table 1: Treating Investigator Global Aesthetic Improvement Scale (GAIS)

3.2.1.4 *Subject Global Aesthetic Improvement Scale (GAIS)*

Treated subjects will evaluate their overall facial aesthetic improvement on the subject GAIS using photographs from Month 2 after the last injection (i.e., either baseline treatment or touch-up, if applicable) and baseline pre-treatment photos for comparison (see Table 2). GAIS will not be completed for subjects randomized to the control group. The subject will be asked: “Considering both IOHs, what is your overall impression of change of your aesthetic result due to treatment, compared to the condition before the injection? Please tick the one option that best fits your overall impression of change.” The following 7-point scale will be used:

Table 2: Subject Global Aesthetic Improvement Scale (GAIS)

3.2.1.5 *FACE-Q instruments* [REDACTED]

Treated and control subjects will evaluate the treatment outcome using FACE-Q instruments (see [Appendix 10.4](#)). [REDACTED]

[REDACTED]

[figure not shown]
[REDACTED] FACE-Q satisfaction with eyes

[REDACTED]

Table 3: FACE-Q satisfaction with eyes

[REDACTED]

[REDACTED]

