5.1 Schedule of events by visit

The Schedule of Events is presented in [Appendices 10.1](#) (treated subjects) and [10.2](#) (control subjects).

Day 0 (-28 Day) – Baseline Treatment (BT) / No Treatment (Control) includes Screening, Enrollment, and Baseline Assessments

[figure not shown]
The following procedures will be performed at this visit in the following order:

- Obtain written informed consent. A subject must be informed of the study requirements, including the risks and benefits of participation. An IEC/IRB-approved informed consent must be signed and dated by the subject prior to any study related activities or procedures being performed, including discontinuation of any prohibited medications.
- Assign subject identification.
- Collect demographic information.
- Collect height and weight. Height will be collected at the baseline visit only.
- Record medical history.
 - Record ocular history.
- Review and record concomitant medications/therapies.
- Perform urine pregnancy test (if female of childbearing potential). Negative test required prior to randomization.
- Confirm subject meets all eligibility criteria.
 - Treating physician confirms that the subject meets all eligibility criteria prior to randomization.
- Take standardized baseline IOH photographs.
- [REDACTED] perform the MIHAS assessment.

[figure not shown]
- Visual safety assessments on both eyes.
 - Visual acuity test (using a Snellen chart);

- Visual field test;
- Ocular motility exam; and
- Fundoscopic (ophthalmoscopic) view of the eye (not dilated).
- Administer FACE-Q assessments to subject.
- Satisfaction with eyes

- Randomize subject.

NOTE: Subjects randomized to the control group (no treatment) have completed this visit and will be scheduled for the Month 2 visit.

- Injection (for subjects randomized to the treatment group):
 - Administer treatment injection **to first IOH**.
- Wait 30 minutes.
- Perform visual safety assessments on first eye (where IOH area was treated).
- Administer treatment injection to second IOH if treating investigator agrees that it is safe to proceed with injecting the second IOH.
- Wait 30 minutes.
- Perform visual safety assessments on other eye (where second IOH area was treated).
- Dispense subject diary and discuss completion instructions.
- Review and record AEs.
- Schedule 72-hour follow-up phone call and Week 2 visit.

Follow-up Phone call (72-hours ±1 day post treatment)

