- Perform urine pregnancy test (if female of childbearing potential and for treated subjects only). Negative test required prior to touch-up injection.
- Injection (only if treating investigator notes asymmetry):
 - Administer touch-up injection **to first IOH.**

- Wait 30 minutes.
- Perform visual safety assessments on first eye (where IOH area was treated).
- Administer treatment injection to second IOH if treating investigator agrees that it is safe to proceed with injecting the second IOH.
- Wait 30 minutes.
- Perform visual safety assessments on other eye (where second IOH area was treated).

NOTE: If only injecting one side, only the side being injected will need the visual safety assessment 30 minutes post treatment.

- Dispense subject diary and discuss completion instructions.

- Review and record AEs.
- Schedule 72-hour follow-up phone call and Week 2 visit.

NOTE: For subjects receiving a touch-up refer to the Follow-up 72 hour Phone Call, Week 2 and Month 1 (safety) assessments as described above. Then subject will continue with Month 2 assessments.

Month 2: Day 56 (+3 days) ALL SUBJECTS

Visit to occur 2 months after last injection (either baseline treatment or touch-up, if applicable) or 2 month after baseline visit for control subjects.

- Review and record changes in concomitant medications/therapies. Confirm subject remains compliant with any applicable study restrictions.
- Perform urine pregnancy test (if female of childbearing potential and for treated subjects only).
- Take standardized IOH photographs.
- Collect weight.
- Review and collect subject diary (touch-up subjects only). The investigator will review the diary and determine if any entries should also be recorded as AEs on the AE eCRF.
- Visual Safety Assessments on both eyes.
 - Visual acuity test (using a Snellen chart);
 - Visual field test;
 - Ocular motility exam; and
 - Fundoscopic (ophthalmoscopic) view of the eye (not dilated).
- [REDACTED] perform MIHAS assessment.

[figure not shown]
- Have the treating investigator complete the investigator GAIS (treated subjects only).

NOTE: Standardized photographs, previously taken during the baseline visit, will be available for the treating investigator to reference when completing the Month 2 GAIS assessment.

- Have subjects complete the subject GAIS (treated subjects only).

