NOTE: Standardized photographs, previously taken during the baseline visit, will be available for the subject to reference when completing his/her Month 2 GAIS assessment.

- Administer FACE-Q assessments to subject.
 - Satisfaction with eyes

- Review and record AEs.
- Schedule and/or confirm Month 3 visit (treated and touch-up subjects only).

Note: This is the last visit for subjects assigned to the control group.

Month 3 (Day 84), 6 (Day 168), 9 (Day 252), and 12 (Day 336) (± 7 days)

- Review and record changes in concomitant medications/therapies. Confirm subject remains compliant with any applicable study restrictions.
- Take standardized IOH photographs.
- Visual Safety Assessments on both eyes.
 - Visual acuity test (using a Snellen chart);
 - Visual field test;
 - Ocular motility exam; and
 - Fundoscopic (ophthalmoscopic) view of the eye (not dilated).
- Review and record AEs.
- Schedule and/or confirm the next visit. Study participation ends after Month 12 visit.

5.1.1 *Scheduled visits*

All scheduled visits and applicable study assessments must occur as noted in [Sections 5.1](#) and the Schedule of Events ([Appendices 10.1](#) (treated subjects) and [10.2](#) (control subjects)).

5.1.2 *Unscheduled visits*

To ensure subject safety during the study, any subject who requires additional follow-up during the study for any reasons (that does not fall on a scheduled study visit) should

have that visit recorded as an unscheduled visit and all applicable CRFs for that unscheduled visit completed. Treated subjects will be followed at 72 hours via a safety follow up phone call. These phone calls may result in an unscheduled visit if any safety concerns are identified. Treated subjects will be completing a diary for 28 days post baseline injection and for 28 days post touch-up injection, which may alert site staff to schedule an unscheduled visit if any safety concerns are identified.

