8.4.1.2 Secondary effectiveness endpoint

[figure not shown]
- For the FACE-Q satisfaction with eyes, sum scores and the equivalent Rasch-transformed scores will be analyzed descriptively for baseline and Month 2 for treatment and control groups. The FACE-Q scale will be scored using a look-up conversion table approach. The scale ranges from 0 to 100 with higher numbers indicating greater satisfaction. The FACE-Q user manual is included in [Appendix 10.4](#), and additional information related to the scoring of the FACE-Q satisfaction with eyes scale will be included in the SAP.
- The investigator GAIS categories will be analyzed descriptively at Month 2 post last injection (i.e., either baseline treatment or touch-up, if applicable) among treated subjects using counts (n) and percentages (%) for each GAIS category

- The responder rates at Month 2 according to the MIHAS, [REDACTED] using subject photographs will be summarized. Treatment response is defined as \geq 1-point improvement on both IOHs compared to baseline.

[figure not shown]

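### The Month 2 visit list puts a treated-only photograph review and self-rated GAIS before FACE-Q, and no visible text fixes the order, so the descriptive between-arm FACE-Q comparison is exposed to an avoidable order effect

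*Protocol*

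**What the plan says.** The Month 2 list in Protocol 5.1 covers all subjects. After the photographs, visual safety assessments and MIHAS come the investigator GAIS (treated only), the subject GAIS (treated only), and then FACE-Q satisfaction with eyes for everyone. The note attached to the subject GAIS reads "Standardized photographs, previously taken during the baseline visit, will be available for the subject to reference when completing his/her Month 2 GAIS assessment". Protocol 3.2.1.4 goes further: treated subjects make the rating using their Month 2 photographs, with the pre-treatment ones for comparison. The item asks "what is your overall impression of change of your aesthetic result due to treatment, compared to the condition before the injection".

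Controls skip this step. Protocol 3.1 states: "No investigator GAIS will be performed with control subjects, nor will these subjects self-report on the GAIS".

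The baseline list in Protocol 5.1 opens with "The following procedures will be performed at this visit in the following order". There, both arms complete FACE-Q before randomization and without a GAIS. The Month 2 list has no such opening sentence.

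On use of the data, Protocol 2.1.1 says: "Responses for FACE-Q satisfaction with eye scores in the control group will be compared to that of the treatment group", with the aim of showing that changes in satisfaction matter clinically to the subject. On analysis, Protocol 8.4.1.2 says that "sum scores and the equivalent Rasch-transformed scores will be analyzed descriptively for baseline and Month 2 for treatment and control groups". SAP 7.1.2 adds change from baseline and a 95% interval for the mean, by arm. No between-arm FACE-Q test is visible in either document.

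**The concern.** A satisfaction score can depend on what the respondent did just before giving it. On the listed sequence, a treated subject looks at before-and-after photographs, answers a question that attributes change to treatment, and then rates satisfaction with the eyes. A control goes to FACE-Q with neither step. The difference in procedure coincides with treatment arm, so no adjustment can separate it from the treatment effect.

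Among the visible endpoints, FACE-Q satisfaction with eyes is the only subject-reported effectiveness measure that both arms complete. The argument in Protocol 2.1.1 about relevance to the subject therefore rests on it. The pilot is also meant to inform a pivotal study, so a distorted contrast, and the procedure that produced it, could carry forward.

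**Working it through.** **The plan's own figures.** The documents give no SD, effect size or power for FACE-Q. The stated power in Protocol 8.1 and SAP 4 (about 80% at 40/20 and about 84% at 44/22) is for Fisher's exact test on MIHAS response, 0.60 versus 0.20. Exact enumeration gives 79.1% and 84.8% with a one-sided p < 0.025 rule, and 81.3% and 87.4% with two-sided p < 0.05. None of these depends on FACE-Q.

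**Step 1: what precedes FACE-Q, by arm and visit (Protocol 5.1, 3.1, 3.2.1.4).**

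| Step listed before FACE-Q | Treated, baseline | Control, baseline | Treated, Month 2 | Control, Month 2 |
|---|---|---|---|---|
| Photographs taken | yes | yes | yes | yes |
| Comparison with baseline photographs | no | no | yes | no |
| Subject GAIS | no | no | yes | no |

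The asymmetry sits in one cell of the arm-by-visit layout.

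**Step 2: does change from baseline remove it?** Let d be the mean shift in FACE-Q caused by doing the GAIS first, and f the fraction of treated subjects assessed in list order. Other biases aside:

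- Expected Month 2 difference (treated minus control) = true effect + f × d.
- Expected baseline difference = 0, by randomization, with no order shift in either arm.
- Expected difference in change from baseline = (true effect + f × d) − 0 = true effect + f × d.

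So it is not removed. If every site follows the list, f = 1 and d enters in full. The documents give neither f nor d, and d could be negative if a subject sees little change in the photographs.

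**Step 3: how large could it be against sampling error?** The SDs and shifts here are assumptions, not figures from the documents. The scale is 0 to 100 (Protocol 8.4.1.2), the group sizes are 44 and 22, and f = 1.

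- SE of the difference = SD × √(1/44 + 1/22) = SD × 0.261.
- 95% half-width = t(0.975, 64 df) × SE.
- Chance that a 95% interval lies wholly above zero with no true effect: upper tail beyond t(0.975, 64 df) of the noncentral t with 64 df and noncentrality d/SE. The nominal value is 2.5%.

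| Assumed SD | SE | Half-width | d = 2 | d = 5 | d = 10 |
|---|---|---|---|---|---|
| 15 | 3.9 | 7.8 | 7.3% | 24.1% | 71.0% |
| 20 | 5.2 | 10.4 | 5.7% | 15.5% | 47.1% |
| 25 | 6.5 | 13.0 | 4.9% | 11.4% | 32.6% |

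In SD units, the shifts are 2/25 to 2/15 = 0.08 to 0.13, 5/25 to 5/15 = 0.20 to 0.33, and 10/25 to 10/15 = 0.40 to 0.67. A negative d of the same size would give the same chances of an interval wholly below zero. The visible plan does not call for a between-arm FACE-Q interval. The table only shows what shift would matter to someone making the comparison announced in Protocol 2.1.1.

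**The case against.** The strongest reply is that a list is not a sequence. The protocol prescribes order for the baseline visit only. Protocol 5.1.1 requires assessments to occur as set out in 5.1, but does not speak of order within a visit. The Month 1 list is plainly not strictly sequential: it schedules the Month 2 visit before the asymmetry assessment that can reset it. The schedules in Appendices 10.1 and 10.2 and the FACE-Q manual in Appendix 10.4 are not in the available text, and much of Protocol 3.2.1.5 is redacted, so a safeguard may exist out of sight. This stands. A reader might infer that the protocol requires all of the roughly 44 treated subjects to do the GAIS first; the documents do not support that. What remains is that a site working down the list would do so, and no visible text protects FACE-Q.

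A reader might also infer that the comparison is known to be biased in favour of treatment. The documents give no evidence that an order effect exists, nor its direction or size.

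The endpoint is secondary and descriptive, in a pilot. That limits the consequence but does not remove it, because a descriptive contrast can also be biased and Protocol 2.1.1 draws a conclusion from this one. SAP 7.1 also allows confidence limits and descriptive p-values where appropriate.

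Finally, other asymmetries remain. Controls are untreated and know it, and only treated subjects keep diaries and attend the Week 2 and Month 1 visits. This is true, but those features come with the design and safety follow-up, whereas the questionnaire order can be changed.

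**Conclusion.** The point holds as a risk to one secondary comparison. The procedural asymmetry is in the text: a treated-only photograph comparison and GAIS are listed ahead of FACE-Q at Month 2, with nothing comparable for controls or at baseline. Whether it shifts scores, and which way, is unknown. If it does, the shift enters the between-arm difference in proportion to how many treated subjects follow the list order, and change from baseline does not cancel it. Under the assumed SDs, a shift of about 5 points is between 0.8 and 1.3 standard errors (5/6.5 to 5/3.9), and a shift of 2 points would matter little.

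Nothing here touches the primary MIHAS comparison, its alpha or the sample size. Reordering would not make the FACE-Q contrast unbiased, since expectation from known allocation stays. The change is still worth making: it removes one avoidable difference from a stated objective at little cost.

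**What to change.** In Protocol 5.1 (Month 2) and in the schedules of events for both arms, state that FACE-Q is completed first, before any photograph is shown to the subject and before either GAIS, and that this order is required. The baseline visit already carries an instruction of this kind.

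The cost is a protocol modification, which under Protocol 9.9 needs written IEC/IRB approval. No assessment, staff or subject is added. There is one trade-off: answering FACE-Q first could influence the subject GAIS, which also feeds the agreement with MIHAS response in Protocol 2.1.1. The GAIS is summarised in treated subjects only, so this would not bias a between-arm contrast.

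SAP 4.1 describes randomization in the past tense, so some or all Month 2 visits may already have taken place. For those subjects, document the order actually used and note the limitation when interpreting the FACE-Q comparison. Whatever can still be changed here, carry the fixed order into the pivotal design.

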5.2 Stopping rules

5.2.1 Criteria for treatment discontinuation

If study treatment is discontinued at any time during the treatment administration, the investigator will record the reason for treatment discontinuation in the study records. The investigator may request that a subject discontinuing treatment will continue to participate in the study and complete all remaining visits and assessments. If a subject declines to continue study participation, the investigator will make every effort to perform the appropriate assessments specified in the Schedule of Events ([Appendices 10.1](#) (treated subjects) and [10.2](#) (control subjects)).

5.2.2 Premature suspension or termination of study

Should the investigator, the sponsor, the FDA, or local regulatory authorities become aware of conditions arising during the conduct of this study that may warrant the cessation of the study, such action may be taken. Prior to such action, consultation between the sponsor, the investigator, and, as appropriate, the FDA and/or local regulatory authorities will occur.

In the case of a treatment related vascular embolic event leading to skin necrosis, vision loss, or stroke, the study will be suspended and a root-cause investigation will be conducted to determine the cause of the embolic event and whether the outcome was anticipated or unanticipated. If the latter situation is observed, the study will be immediately suspended and no subjects will be enrolled or treated until the event can be properly characterized and an appropriate treatment strategy to avoid this unanticipated event can be devised.

Reasons for the premature suspension or termination of the study include, but are not limited to, the following:

- Determination of a potential safety risk to subjects;
- Inadequate subject enrollment;
- Decision by the IEC/IRB to suspend or terminate approval/favorable opinion for the study;

- Sponsor decision; and/or
- Other.

In the event of premature study suspension or termination for safety reasons, the sponsor will inform all investigators and relevant regulatory authorities promptly of the study suspension/termination and reason for the action. The investigator will conduct site closure activities in accordance with all applicable sponsor and local/international guidelines and regulations.

5.2.3 *Study site discontinuation*

Study participation by individual sites may be discontinued by the sponsor for any of the reasons listed in [Section 5.2.2](#). Additional reasons for the premature discontinuation of study sites include, but are not limited to, the following:

- Investigator request;
- Serious or persistent noncompliance with the protocol, local regulations and/or GCP;
- Failure to accrue subjects at an acceptable rate;
- Ethical issues; and/or
- Other

In the event of study site discontinuation, the sponsor will provide to the study site written notification documenting the reason for discontinuation. The investigator will conduct site closure activities in accordance with all applicable sponsor and local/international guidelines and regulations.

5.2.4 *Discontinuation criteria for a subject*

Each subject will be followed to the end of the study, or/if when the sponsor decides to terminate the study, whichever comes first. The only reasons a subject will not be followed for all scheduled visits are withdrawal of consent, lost to follow-up (e.g., moving away from study site; unresponsive to attempts to contact the subject), any AE or adverse device effect (ADE).

If a subject withdraws consent to continue in the study, the investigator should make every attempt to complete the final study visit. If a non-serious AE is unresolved at the time of the subject's final study visit, an effort will be made to follow-up until the AE is resolved or stabilized, the subject is lost to follow-up, or there is some other resolution of this event. The investigator should make every attempt to follow all serious adverse events (SAEs)/unanticipated adverse drug effects (UADEs) to resolution. Information on

pregnancy and the outcome for any woman who becomes pregnant during the study will be collected. Additional information on subject withdrawal criteria is provided in [Section 4.6](#).

5.2.5 *Provision of care for subjects after study discontinuation*

The investigator is responsible for ensuring the adequate and safe medical care of subjects during the study. After completion of the study, the sponsor will follow all applicable local or international regulations and guidelines with regard to follow-up treatment for subjects. The investigator will ensure that appropriate consideration is given to a subject's post-study care.

